## 8. Sensitivity analyses

### 1) Impact of protocol amendment 2 - Use of SPECT

The prevalence of patients with cardiac fixation at the radionuclide bone scintigraphy and/or Single Photon Emission Computed Tomography (SPECT) performed with 99mTc-DPD or 99mTc-PYP or 99mTc-HMDP\* among patients with (left ventricular hypertrophy) LVH from undiagnosed etiology will be calculated in patients included before protocol amendment and in patients included after protocol amendment (Amendment 2 – Date: 11-Feb-2020). The percentage and its 95% CI will be provided.

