## 5. AMENDMENTS AND UPDATES

Amendment number	Date	Protocol section(s) changed	Summary of amendment(s)	Reason
N°1	14 JUN 2018			New European legislation
N°2	11 FEBRUARY 2020	Inclusion/ Exclusion criteria Variables CRF ICD Milestone	Clarification of the protocol process to be in line with the requirement of a NIS protocol Addition of the SPECT in the inclusion criteria Inclusion period extension	Protocol clarification and deletion of the biological sample collection
N°2.1	22 OCTOBER 2020	Milestone	Extension for the data collection	Due to the international pandemic and to allow to reach the goal of the number of patient screened, it was decided to extend the inclusion period
N°2.2	21 MAY 2021	Milestone	Extension for the inclusion period and data collection	Due to the international pandemic and to allow to reach the goal of a minimum of one thousand patient screened, it was decided to extend the inclusion period. Participating country list updates
N°2.3	04 NOVEMBER 2021	Milestone	Extension for the inclusion period and data collection	Due to the international pandemic and to allow to reach the goal of a minimum of one thousand patient screened, it was decided to extend the inclusion period.

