**Figure 2. Study Flow Chart**

**9. RESEARCH METHODS**

## 9.1. Study Design

TTRACK is an epidemiological multicenter and multinational study.

Patients can be enrolled from several countries listed in Appendix 5. This list is non-exhaustive and additional countries may be added to this list.

The management of this protocol will be aligned with country legislation and regulatory procedures.

Investigators will be cardiologists experienced in diagnosis of cardiomyopathies or physicians specialized in diagnosing patients with LVH. The sites involved (at least when performing feasibility) will be representative of their respective country in terms of practice. Participating physicians will not be influenced in their decision making and routine proceedings in any way.

The study will include approximately 1500 patients.

All assessments described in this protocol are performed as part of routine clinical practice or standard practice guidelines for the patient population and healthcare provider specialty in the countries where this non-interventional study is being conducted. Data, including individual study results, will be collected from these assessments, if performed.

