#### 9.5. Study Size

Considering a prevalence of ATTR-CM around 10%, the screening of N =1500 patients will provide a precision of  $\pm 1.5\%$  in the estimation of this prevalence with a 95% two-sided confidence interval (first objective). In addition, considering such a prevalence, the precision of the estimation of the different symptoms or additional signs within the population of ATTR-CM (other objectives) will be estimated with a precision of  $\pm 7.3\%$  for any sign/symptom with a frequency of 30% or lower.

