## 1 AMENDMENTS FROM PREVIOUS VERSION(S)

Version	Effective Date	Change Type (New, Revise, Admin)	Summary of Revisions
1	27-Apr-2020	New	
2	06-Jul-2022	Revise	
 
• Wording modified in line with clarifications in protocol amendment 2
 
• To add sensitivity analyses to assess the impact of:               
 
○ using a SPECT
 
○ no longer using a centralized lab
 
 
 
• Subgroups analyses added
 
• To add scintigraphy discrepancies analysis
 

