## **8 STATISTICAL METHODOLOGY AND STATISTICAL ANALYSES**

### **8.1 STATISTICAL METHODS**

Quantitative variables will be described using number of filled and missing data, mean, standard deviation, median, 1st and 3rd quartiles, minimum and maximum. The 95%CI of the mean will also be provided, assuming a normal distribution. In case of departure from normality, results will be interpreted based on median and Interquartile Range (IQR).

Qualitative variables will be described using number of filled and missing data and, for each modality, the frequency and percentage (referring to filled data). A 95% confidence interval (CI) will be associated to binomial proportions using the Wilson score method.

Factors associated to an outcome of interest (ATTR vs other and ATTRwt vs ATTRv within patients diagnosed with ATTR-CM) will be identified using univariate logistic regression models. A separate logistic regression model will be created for each factor (as well as covariates described in section 6.4). If the variable is significantly associated to the outcome at the 10% level then the factor will be put forward into a multivariate model. Once the univariate model selection is complete, backwards selection will be used to remove factors from the multivariate model which do not have a significant p value at the 5% level. The covariate with the highest p value will be removed in turn until all factors have a p value less than 0.05. If a significant interaction is found then the individual factors of this interaction will be kept in the model, regardless of their p value. A significant interaction is tested for between all variables in the multivariate model.

Furthermore, a table showing all of the 95% confidence intervals and p values for the odds ratios coming from the univariate and multivariate models will be created.

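### The SPECT sensitivity analysis gives two crude prevalences by inclusion date, with no estimated difference, no control for site or country mix and no use of the modality actually performed, so it cannot show the impact of SPECT.

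*SAP*

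**What the plan says.** SAP section 1 gives the reason for the analysis. Version 2 was revised "To add sensitivity analyses to assess the impact of" two changes, the first being the use of SPECT. Under section 8.2 (Other analyses, item 8, part 1) the prevalence of cardiac fixation "will be calculated in patients included before protocol amendment and in patients included after protocol amendment (Amendment 2 – Date: 11-Feb-2020", and then: "The percentage and its 95% CI will be provided". That is the whole specification.

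SAP section 8.1 supplies the interval, which "will be associated to binomial proportions using the Wilson score method". This is an interval for one proportion; no method is given for a difference between two. Neither site nor country appears among the covariates in section 6.4 or the subgroups in section 5.3.

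Three protocol provisions bear on who was enrolled when:
- Section 5 records, for Amendment 2.2 (21 May 2021), "Participating country list updates".
- Section 9.1 says of the countries: "This list is non-exhaustive and additional countries may be added to this list".
- Section 9.2.2 caps each site at 100 screened patients.

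The protocol's section 9.3 lists SPECT date and SPECT result as variables separate from the scintigraphy grade.

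**The concern.** An analysis of impact should produce an estimate of impact, and this one does not. There are three gaps.

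1. **No contrast.** The reader gets two intervals and has to compare them by eye. Treating overlap as evidence of no difference is too conservative.
2. **No control for mix.** If the later patients come from different sites or countries, a change in referral pattern can look like a SPECT effect or hide one.
3. **The wrong exposure.** The groups are defined by calendar date, not by imaging. The inclusion criteria allow scintigraphy and/or SPECT, so some later patients may have had planar imaging only. Amendment 2 also changed eligibility criteria, variables and the CRF, and SAP section 1 ties the end of the centralized laboratory to the same amendment. The protocol date need not be the date on which a site adopted the amendment.

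At stake is whether a reader can tell if widening the imaging criterion moved the prevalence of fixation, which the primary endpoint counts on either modality.

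**Working it through.** **The plan's own figure.** Protocol section 9.5 takes an ATTR-CM prevalence near 10% with N = 1500 and states a half-width of ±1.5 points. It ties this figure to the primary question: "in the estimation of this prevalence with a 95% two-sided confidence interval (first objective". The half-width is 1.96 × √(p(1−p)/n). With p = 0.10 and n = 1500 this is 1.96 × √(0.09/1500) = 1.52 points, so the figure reproduces. It describes one pooled prevalence of 10%. At 20% and 25% the same formula gives 2.02 and 2.19 points. No precision is stated for the before/after analysis.

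**Do two intervals stand in for a difference?** The documents give no split. Assume 750 per period and the planning prevalence of 10% before.
- Before: 75/750 = 10.0%, Wilson 95% CI 8.1 to 12.4.
- After: 101/750 = 13.5%, Wilson 95% CI 11.2 to 16.1.
- The intervals overlap.
- Difference: 13.47 − 10.00 = 3.47 points. SE = √(0.1000×0.9000/750 + 0.1347×0.8653/750) = 1.66 points. 95% CI 3.47 ± 1.96 × 1.66 = 0.2 to 6.7.

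Overlap and a difference that excludes zero can therefore coexist. The particular result depends on size: at 500 per period, 10.0% and 13.5% give a difference of 3.5 points (95% CI −0.5 to 7.5).

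**Precision of the missing contrast.** Half-width = 1.96 × √(0.09/n₁ + 0.09/n₂), assuming 10% in both periods. N = 1500 is the planned size; 1000 is the minimum goal named in the later amendments.

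| Total N | Split 50:50 | Split 30:70 or 70:30 |
|---|---|---|
| 1500 | ±3.0 points | ±3.3 points |
| 1000 | ±3.7 points | ±4.1 points |

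On the same splits, a rise from 10% has 80% power only if it reaches 14.8–15.3% (N = 1500) or 16.0–16.7% (N = 1000).

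**Can mix alone matter at that scale?** Assume two kinds of site, with 5% and 20% prevalence.
- No SPECT effect, share of low-prevalence sites falling from 70% to 50%: 0.7×5 + 0.3×20 = 9.5%, then 0.5×5 + 0.5×20 = 12.5%. This is an apparent rise of 3.0 points. With a fall to 40%, the later figure is 14.0%, a rise of 4.5 points.
- True odds ratio 1.5, low-prevalence share rising from 50% to 75%: the strata become 7.3% and 27.3%, and the crude prevalence goes from 12.5% to 0.75×7.3 + 0.25×27.3 = 12.3%. The effect disappears.

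These strata are invented to show what is possible. They are not estimates for this study.

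**Date against modality.** The protocol's Annex 2, for the DPD tracer, describes SPECT as a further acquisition in patients who already show uptake. Where that sequence is followed, SPECT cannot turn a negative planar scan into a positive patient. The quantity that speaks directly to SPECT's contribution is the number of patients positive on SPECT but not on planar imaging, and no comparison by inclusion date yields it.

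**The case against.** The strongest reply is that the study is declared mainly descriptive, with exploratory tests and no inferential hypothesis (SAP sections 4.1 and 4.2). Anyone given two percentages and their denominators can compute the crude difference. That stands as far as it goes: the missing crude contrast is easily repaired. But no reader can remove site or country mix from published totals, or recover modality from inclusion date. A difference with a CI is an estimate and sits comfortably in a descriptive plan, which already includes multivariable logistic models.

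Second, the evidence for a changed mix is indirect, and this stands. A reader might infer that the two periods did contain different sites and countries. The documents do not say so. The amendment log records a country-list update without saying what changed, countries may be added, and nothing shows that any site reached its cap. The supportable statement is that the mix may differ.

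Third, the SAP also describes all CRF variables by grade in FAS1, which should include SPECT data. That is some information, but it does not estimate impact.

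Finally, a reader might take this check to be what justifies pooling the primary prevalence across Amendment 2. No passage makes pooling depend on it.

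**Conclusion.** The point holds for this sensitivity analysis: as specified it cannot show the impact of SPECT. It provides no contrast, leaves possible differences in site or country mix uncontrolled, and uses calendar period in place of imaging modality. The last is the most basic gap, because even a well-adjusted before/after comparison estimates the effect of the amendment period.

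On size, the unrestricted crude difference would carry a 95% half-width of about ±3 to ±4 points, assuming 10% prevalence, N of 1000 to 1500 and splits of 30:70 to 70:30. Under invented strata, shifts in mix could produce or conceal changes of that order. The documents do not show that they did. It would also be wrong to set such shifts against the protocol's ±1.5 points, which belongs to a single pooled 10% prevalence. Nothing here shows that the primary estimate is wrong, and it is unchanged by the fix.

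**What to change.** In SAP section 8.2, Other analyses, item 8, part 1:

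1. Keep the two period percentages with their Wilson CIs, as description.
2. Add the after-minus-before difference (or odds ratio) with its 95% CI, adjusted for age, sex and country or site. Label it an amendment-period effect.
3. Repeat it in sites that enrolled in both periods. Countries or sites active in one period only contribute nothing to a contrast adjusted for them, so the restriction makes plain who informs the result.
4. Tabulate cardiac fixation by modality actually used (planar only, SPECT only, both), with the number positive on SPECT alone.

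The cost is one model, its repeat and one table. Centre number, birth month and year, gender, visit date, scintigraphy grade and SPECT result are already listed for collection. The common-sites comparison will be less precise than the ±3 to ±4 points above, by an amount that cannot be given without the enrolment by site. Amendment 2 changed the CRF, and the documents do not say whether SPECT fields existed before it, so the modality table should show missing data by period.

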### 2) Impact of protocol amendment 2 – No longer using a centralized lab

The prevalence of patients with laboratory signs will be calculated in patients included before protocol amendment and in patients included after protocol amendment (Amendment 2 – Date: 11-Feb-2020). The percentage and its 95% CI will be provided.

**9 LIST OF TABLES AND TABLE SHELLS**

A list of tables will be provided in a separate document. An example of some table shells is presented below:

**Table 15.1.1 Number and Percentage of Patients in Each Analysis Set**

Analysis Set		Grade 0 (N=XX)	Grade 1 (N=XX)	Grade 2 (N=XX)	Grade 3 (N=XX)	Unknown grade (N=XX)	Total (N=XX)
Selected	No						xx (xx.x%)
	Yes						xx (xx.x%)
FAS1	No	xx (xx.x%)	xx (xx.x%)	xx (xx.x%)	xx (xx.x%)	xx (xx.x%)	xx (xx.x%)
	Yes	xx (xx.x%)	xx (xx.x%)	xx (xx.x%)	xx (xx.x%)	xx (xx.x%)	xx (xx.x%)
FAS2	No		xx (xx.x%)	xx (xx.x%)	xx (xx.x%)	xx (xx.x%)	xx (xx.x%)
	Yes		xx (xx.x%)	xx (xx.x%)	xx (xx.x%)	xx (xx.x%)	xx (xx.x%)
FAS3	No		xx (xx.x%)	xx (xx.x%)	xx (xx.x%)	xx (xx.x%)	xx (xx.x%)
	Yes		xx (xx.x%)	xx (xx.x%)	xx (xx.x%)	xx (xx.x%)	xx (xx.x%)
FAS4	No		xx (xx.x%)	xx (xx.x%)	xx (xx.x%)	xx (xx.x%)	xx (xx.x%)
	Yes		xx (xx.x%)	xx (xx.x%)	xx (xx.x%)	xx (xx.x%)	xx (xx.x%)
Safety Set	No	xx (xx.x%)	xx (xx.x%)	xx (xx.x%)	xx (xx.x%)	xx (xx.x%)	xx (xx.x%)
	Yes	xx (xx.x%)	xx (xx.x%)	xx (xx.x%)	xx (xx.x%)	xx (xx.x%)	xx (xx.x%)

...

**Table 15.1.2 Demography and Baseline Characteristics – FAS1, 2**

Variables		FAS 2					Total (FAS 1)
		Grade 0	Grade 1	Grade 2	Grade 3	Grade 1 or 2 or 3	
		(N=XX)	(N=XX)	(N=XX)	(N=XX)	(N=XX)	
Age (years)	N	xx	xx	xx	xx	xx	xx
	Mean ± SD	xx.x ± x.x	xx.x ± x.x	xx.x ± x.x	xx.x ± x.x	xx.x ± x.x	xx.x ± x.x
	Median	xx.x	xx.x	xx.x	xx.x	xx.x	xx.x
	Q1 ; Q3	xx.x ; xx.x	xx.x ; xx.x	xx.x ; xx.x	xx.x ; xx.x	xx.x ; xx.x	xx.x ; xx.x
	Min. ; Max.	xx ; xx	xx ; xx	xx ; xx	xx ; xx	xx ; xx	xx ; xx
	Missing	x	x	x	x	x	x
Age (in class)	[50 - 55] years	xx (xx.x%)	xx (xx.x%)	xx (xx.x%)	xx (xx.x%)	xx (xx.x%)	xx (xx.x%)
	]55 - 60] years	xx (xx.x%)	xx (xx.x%)	xx (xx.x%)	xx (xx.x%)	xx (xx.x%)	xx (xx.x%)
	]60 - 65] years	xx (xx.x%)	xx (xx.x%)	xx (xx.x%)	xx (xx.x%)	xx (xx.x%)	xx (xx.x%)
	]65 - 70] years	xx (xx.x%)	xx (xx.x%)	xx (xx.x%)	xx (xx.x%)	xx (xx.x%)	xx (xx.x%)
	]70 - 75] years	xx (xx.x%)	xx (xx.x%)	xx (xx.x%)	xx (xx.x%)	xx (xx.x%)	xx (xx.x%)

PFIZER CONFIDENTIAL

	[75 - 80] years	xx (xx.x%)	xx (xx.x%)	xx (xx.x%)	xx (xx.x%)	xx (xx.x%)	xx (xx.x%)
	over 80 years	xx (xx.x%)	xx (xx.x%)	xx (xx.x%)	xx (xx.x%)	xx (xx.x%)	xx (xx.x%)
Gender	Missing	xx	xx	xx	xx	xx	xx
	Male	xx (xx.x%)	xx (xx.x%)	xx (xx.x%)	xx (xx.x%)	xx (xx.x%)	xx (xx.x%)
	Female	xx (xx.x%)	xx (xx.x%)	xx (xx.x%)	xx (xx.x%)	xx (xx.x%)	xx (xx.x%)
Weight (kg)	N	xx	xx	xx	xx	xx	xx
	Mean ± SD	xx.x ± x.x	xx.x ± x.x	xx.x ± x.x	xx.x ± x.x	xx.x ± x.x	xx.x ± x.x
	Median	xx.x	xx.x	xx.x	xx.x	xx.x	xx.x
	Q1 ; Q3	xx.x ; xx.x	xx.x ; xx.x	xx.x ; xx.x	xx.x ; xx.x	xx.x ; xx.x	xx.x ; xx.x
	Min. ; Max.	xx ; xx	xx ; xx	xx ; xx	xx ; xx	xx ; xx	xx ; xx
	Missing	x	x	x	x	x	x
BMI (kg/m  )	N	xx	xx	xx	xx	xx	xx
	Mean ± SD	xx.x ± x.x	xx.x ± x.x	xx.x ± x.x	xx.x ± x.x	xx.x ± x.x	xx.x ± x.x
	Median	xx.x	xx.x	xx.x	xx.x	xx.x	xx.x
	Q1 ; Q3	xx.x ; xx.x	xx.x ; xx.x	xx.x ; xx.x	xx.x ; xx.x	xx.x ; xx.x	xx.x ; xx.x
	Min. ; Max.	xx ; xx	xx ; xx	xx ; xx	xx ; xx	xx ; xx	xx ; xx
	Missing	x	x	x	x	x	x

...

Table 15.1.2 Demography and Baseline Characteristics – FAS 2&3

Variables	Grade 1 (N=XX)	FAS 3					Total (=FAS 2)
		ATTRwt (N=XX)	ATTRv (N=XX)	ATTR (=FAS 3.1) (N=XX)	FAS 3.2 (N=XX)	All FAS 3 (N=XX)	
Age (years)	N	xx	xx	xx	xx	xx	xx
	Mean ± SD	xx.x ± x.x	xx.x ± x.x	xx.x ± x.x	xx.x ± x.x	xx.x ± x.x	xx.x ± x.x
	Median	xx.x	xx.x	xx.x	xx.x	xx.x	xx.x
	Q1 ; Q3	xx.x ; xx.x	xx.x ; xx.x	xx.x ; xx.x	xx.x ; xx.x	xx.x ; xx.x	xx.x ; xx.x
	Min. ; Max.	xx ; xx	xx ; xx	xx ; xx	xx ; xx	xx ; xx	xx ; xx
	Missing	x	x	x	x	x	x
Age (in class)	[50 - 55] years	xx (xx.x%)	xx (xx.x%)	xx (xx.x%)	xx (xx.x%)	xx (xx.x%)	xx (xx.x%)
	[55 - 60] years	xx (xx.x%)	xx (xx.x%)	xx (xx.x%)	xx (xx.x%)	xx (xx.x%)	xx (xx.x%)
	[60 - 65] years	xx (xx.x%)	xx (xx.x%)	xx (xx.x%)	xx (xx.x%)	xx (xx.x%)	xx (xx.x%)

PFIZER CONFIDENTIAL

	]65 - 70] years	xx (xx.x%)	xx (xx.x%)	xx (xx.x%)	xx (xx.x%)	xx (xx.x%)	xx (xx.x%)	xx (xx.x%)
	]70 - 75] years	xx (xx.x%)	xx (xx.x%)	xx (xx.x%)	xx (xx.x%)	xx (xx.x%)	xx (xx.x%)	xx (xx.x%)
	]75 - 80] years	xx (xx.x%)	xx (xx.x%)	xx (xx.x%)	xx (xx.x%)	xx (xx.x%)	xx (xx.x%)	xx (xx.x%)
	over 80 years	xx (xx.x%)	xx (xx.x%)	xx (xx.x%)	xx (xx.x%)	xx (xx.x%)	xx (xx.x%)	xx (xx.x%)
Gender	Missing	xx	xx	xx	xx	xx	xx	xx
	Male	xx (xx.x%)	xx (xx.x%)	xx (xx.x%)	xx (xx.x%)	xx (xx.x%)	xx (xx.x%)	xx (xx.x%)
	Female	xx (xx.x%)	xx (xx.x%)	xx (xx.x%)	xx (xx.x%)	xx (xx.x%)	xx (xx.x%)	xx (xx.x%)
Weight (kg)	N	xx	xx	xx	xx	xx	xx	xx
	Mean ± SD	xx.x ± x.x	xx.x ± x.x	xx.x ± x.x	xx.x ± x.x	xx.x ± x.x	xx.x ± x.x	xx.x ± x.x
	Median	xx.x	xx.x	xx.x	xx.x	xx.x	xx.x	xx.x
	Q1 ; Q3	xx.x ; xx.x	xx.x ; xx.x	xx.x ; xx.x	xx.x ; xx.x	xx.x ; xx.x	xx.x ; xx.x	xx.x ; xx.x
	Min. ; Max.	xx ; xx	xx ; xx	xx ; xx	xx ; xx	xx ; xx	xx ; xx	xx ; xx
	Missing	x	x	x	x	x	x	x
BMI (kg/m  )	N	xx	xx	xx	xx	xx	xx	xx
	Mean ± SD	xx.x ± x.x	xx.x ± x.x	xx.x ± x.x	xx.x ± x.x	xx.x ± x.x	xx.x ± x.x	xx.x ± x.x
	Median	xx.x	xx.x	xx.x	xx.x	xx.x	xx.x	xx.x
	Q1 ; Q3	xx.x ; xx.x	xx.x ; xx.x	xx.x ; xx.x	xx.x ; xx.x	xx.x ; xx.x	xx.x ; xx.x	xx.x ; xx.x
	Min. ; Max.	xx ; xx	xx ; xx	xx ; xx	xx ; xx	xx ; xx	xx ; xx	xx ; xx
	Missing	x	x	x	x	x	x	x

...

Table 15.2.1 Prevalence of Patients with Cardiac Fixation at the Radionuclide Bone Scintigraphy and / or SPECT Performed – FAS1

Variable(s)	Total (N=XX)
Prevalence of patients with cardiac fixation at the radionuclide bone scintigraphy and /or SPECT performed	xx (xx.x%)
	IC95% [xx.x% - xx.x%]

...

Table 15.2.2 Factors Associated to Positive Scintigraphy (Logistic Regression Model) – FAS1

Explanatory Variable	Positive Scintigraphy		Univariate Analysis		Multivariate Analysis	
	Yes (N=xx)	No (N=xx)	Odds-Ratio [95% CI]	p-value	Odds-Ratio [95% CI]	p-value
n	xx	xx				
Missing data	x	x				
Factor 1 (qualitative)				x.xxx		x.xxx
Modality 1 (reference)	xx (xx.x%)	xx (xx.x%)	1.00		1.00	
Modality 2	xx (xx.x%)	xx (xx.x%)	x.xx [x.xx;x.xx]		x.xx [x.xx;x.xx]	
Factor 2 (quantitative)				x.xxx		x.xxx
Mean (SD)	xx.x (xx.x)	xx.x (xx.x)				
Per XX-unit increment			x.xx [x.xx;x.xx]		x.xx [x.xx;x.xx]	

## 10 REFERENCES

NA

## 11 APPENDICES

### 11.1 APPENDIX 1: DATA DERIVATION DETAILS

Age = (Patient screening visit date – Birthdate + 1) /365.25 , where day of birth is imputed to 15, as only month and year of birth are recorded.

Diastolic Blood Pressure classes:

- < 60 mmHg,
- [61 – 70] mmHg,
- [71 – 80] mmHg,
- [81 – 90] mmHg,
- [91 – 100] mmHg,
- > 100 mmHg.

Heart Rate classes:

- < 50 bpm,
- [51 – 60] bpm,
- [61 – 70] bpm,
- [71 – 80] bpm,
- [81 – 90] bpm,
- [91 – 100] bpm,
- [101 – 120] bpm,
- > 120 bpm.

PR interval classes:

- [90 – 100] ms
- [101 – 110] ms
- [111 – 120] ms
- [121 – 130] ms
- [131 – 140] ms
- [141 – 150] ms
- [151 – 160] ms
- [161 – 170] ms
- [171 – 180] ms
- [181 – 190] ms
- [191 – 200] ms
- [201 – 210] ms
- [211 – 220] ms
- [221 – 230] ms

- [231 – 240] ms
- [241 – 250] ms
- [251 – 260] ms
- [261 – 270] ms
- [271 – 280] ms
- > 280 ms

Serum Free Light Chain Ratio:

sFLC Ratio = Kappa / Lambda,

sFLC ratio classes:

- < 0.26,
- [0.26 – 1.65],
- > 1.65.

Abnormal values for all quantitative variables will be defined after medical advise.
